13. Each patient must be assessed for capacity to consent by the principal or sub-investigators in order to provide informed consent. If the patient is deemed unable to provide informed consent, they must have a legally authorized representative (LAR), and the LAR must review and sign the informed consent form. If the patient does not have a LAR, the patient must appear able to provide informed consent and must review and sign the informed consent form. If the patient is deemed unable to provide informed consent and does not have a LAR, they cannot participate in the study. In addition, the patient's study partner/informant (as defined in the study inclusion criteria) must sign the informed consent form. If the LAR and the patient's study partner/informant are the same individual, he/she should sign under both.
14. No active suicidality identified on Columbia-Suicide Severity Rating Scale (C-SSRS).
15. Patients with stable prostate cancer may be included at the discretion of the Medical Monitor.
16. Patients who are on monoclonal antibody medication for the treatment of Alzheimer's (ex. lecanemab, donanemab) for > 6 months or have discontinued monoclonal antibody medication for the treatment of Alzheimer's for > 6 months may be included if all other criteria have been met.

Exclusion Criteria

Subjects will be excluded if they have any of the conditions listed below:

1. Taking one of the following medications: Medications for treatment of cancer or other drugs that weaken the immune system (ex. Natalizumab and Rituximab), Amiodarone, Bishydroxycoumarin, Chloramphenicol, Cimetidine, Fluconazole, Fluvastatin, Miconazole, Phenylbutazone, Sulphinpyrazone, Sulphadiazine, Sulphamethizole, Sulfamethoxazole, Sulphaphenazole, Trimethoprim, and Zafirlukast.
2. Current active infection in participants including, but not limited to, herpes zoster, herpes infection, bronchitis, sinusitis, upper respiratory infection and fungal skin infection. Siponimod may increase the risk in participants with active infections.
3. If participant received mRNA COVID-19 vaccination, must have received last dose at least 3 months prior to first dose of study drug/placebo.
4. Current evidence or history within the last 3 years of a neurological or psychiatric illness that could contribute to

dementia, including (but not limited to) epilepsy, focal brain lesion, Parkinson's disease, seizure disorder, or head injury with loss of consciousness.

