5. STUDY DESIGN

OVERALL DESIGN

In the current project we aim to test the **central hypothesis that Siponimod could lower the rate of neurodegeneration as measured by brain atrophy in mild AD dementia subjects**. To test our central hypothesis, we will carry out an 18-month Phase II, double-blind, randomized, two-armed, placebo controlled, proof-of-concept clinical study in 105 mild AD dementia subjects who will receive an escalating dose of Siponimod (0.25-1 mg/day) or placebo at a randomization ratio of 2:1 for 12 months, followed by a 6-month washout period. For patients who meet inclusion/exclusion criteria, 35 will be randomly assigned to the placebo group, and 70 will be randomly assigned to the drug arm. A single site will manage the entire study, i.e. the Barrow Neurological Institute (BNI) in Phoenix, AZ. No patient stratification and no interim analysis are planned. The decision to pursue dosing will depend on safety data which is included in the inclusion/exclusion criteria.

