6. SCIENTIFIC RATIONALE FOR STUDY DESIGN

This is a randomized, double-blind, placebo-controlled, parallel group study. The use of placebo is appropriate to minimize bias related to treatment expectations of the subject, study partner, and site investigator, as well as bias related to changes in the relationship between the subject and study partner that might occur with the initiation of treatment and expectation of improvement in motor symptoms or cognition. Changes in subject /study partner interactions can impact subject mood and might introduce biases that cannot be quantified. The double-blind use of placebo will also prevent bias in the clinical and scientific assessments.

Most monotherapy clinical trials with a focus on disease modification completed to date have failed to meet the clinical endpoint of significantly slowing cognitive decline in dementia due to Alzheimer's disease (AD), including BACE1 inhibitors⁴⁰, γ -secretase inhibitors and modulators¹⁸, and active and passive immunization against monomeric, oligomeric, and protofibril A β ²⁶. Recently the mABs, aducanumab and lecanemab, were approved on the biomarker endpoints of removing amyloid. This emphasizes the urgent need for novel therapeutic approaches able to reduce several AD neuropathologies simultaneously.

Inflammation is prominent in many neurological disorders, yet no clinical trial has demonstrated the efficacy of anti-inflammatory agents for AD. Interestingly, chronic peripheral low-grade inflammation is associated with aging and increases the risk for disease and mortality, including the development of AD²⁰. Accumulating evidence indicates that nuclear factor- κ B (NF- κ B), tumor necrosis factor alpha (TNF- α), interleukins (e.g. IL-1 β , IL-2, and IL-6), and chemokines (e.g. IL-8) were found elevated both in the blood and central nervous system (CNS) of AD patients²⁰. These data confirm that inflammation plays a critical role in the cause and effect of AD neuropathology⁴². Interestingly, Siponimod is capable of modulating inflammation by preventing egression of lymphocytes from lymphoid organs, and the modulation of cytokine expression, including in microglia⁵.

The use of the NIA-AA criteria³² is well-established and accepted for the diagnosis of mild AD. Nonetheless, we will use eventual updates released by the NIA for the diagnosis of AD throughout the duration of our clinical study.

Safety will be assessed by standard measures throughout the study.

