At the baseline visit (Visit 2), subjects who have met all the eligibility criteria for enrollment will be randomly assigned to one of two treatment groups:

1. Placebo (n=35) or
2. Siponimod 1 mg/day (n=70)

Randomization will be 2:1 and designed by our biostatistician. Randomization will take place during the Baseline visit.

In case of toxicity finding, the blinding will remain in effect as neither the Investigator, nor site staff will be informed whether the participants receive Siponimod or placebo. However, the study pharmacist will be informed in case there is need to adjust dosing if participants are treated with investigational product.

An independent statistician supporting the DSMB will be unblinded and may unblind the DSMB if required for proper study monitoring. All staff and research personnel involved in this study will remain blinded until all subjects have completed the trial and scientific data acquired.

STUDY INTERVENTION COMPLIANCE

Patient compliance with study medication will be assessed at each visit. Compliance will be assessed by direct questioning and counting returned tablets. Deviation(s) from the prescribed dosage regimen should be recorded in the CRF.

Patients who are significantly noncompliant will be instructed to discontinue medication from the study. A patient will be considered significantly noncompliant if he or she misses more than 21 consecutive days of study medication during the study without extenuating circumstance, for example: development of an SAE. Patients who stop dosing due to development of an SAE will have their case reviewed by investigator, site, medical monitor, DSMB, and Principal Investigator for prescribing appropriate actions. Similarly, a patient will be considered significantly noncompliant if he or she is judged by the investigator to have intentionally or repeatedly taken more than the prescribed amount of medication. Drug accountability will be emphasized at the start-up meeting, and drug accountability will be monitored throughout the study.

Temporary discontinuation of treatment with study drug due to ARIA-E should not be considered as non-compliance.

CONCOMITANT THERAPY

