All concomitant medications taken during the study must be recorded on the concomitant medications case report form (CRF). Patients and their study partners/ caregivers will be instructed to consult the investigator or other appropriate study personnel at the site before initiation of any new medications or supplements and before changing dose of any current concomitant medications or supplements.

Medications that may affect cognitive function should be discussed with the medical monitor to determine if the patient should remain in the study.

- Allowed Concomitant Therapy

Patients on stable standard of care (SoC) AD treatment will be allowed in the study. The patient can be on stable doses of a cholinesterase inhibitor and/or memantine if it is stable for at least 90 days prior to the screening visit and is expected to remain on a stable dose for the remainder of the study period; or have demonstrated intolerance to or lack of efficacy from these medications.

- Prohibited Concomitant Therapy

Any therapy that does not fit with the SoC will be prohibited, including, but not limited to, cancer chemotherapy, narcotics, antimanic, and any anticonvulsants/antiseizures taken specifically for seizure disorders or epilepsy, and drugs listed in the exclusion criteria.

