12. STATISTICAL CONSIDERATIONS

STATISTICAL HYPOTHESES

- Primary and Exploratory Efficacy Endpoint(s):

The null hypothesis for the primary efficacy endpoint is that biomarker measures (primary endpoint: vMRI; tertiary and exploratory endpoints: CSF biomarkers, blood inflammatory markers, saliva amyloid beta levels) will be the same in Siponimod- vs. placebo-treated study subjects after 12 months (end of dosing).

The alternative hypothesis is that Siponimod will improve biomarker measures at the same time point.

- Secondary Efficacy Endpoint(s):

The null hypothesis for the secondary efficacy endpoint is that cognitive measures (ADCOMS) will be the same in Siponimod - vs. placebo-treated study subjects after 12 (end of dosing) and 18 months (6 months follow up).

The alternative hypothesis is that Siponimod will improve cognitive measures at the same time points.

SAMPLE SIZE DETERMINATION

Mild AD subjects will receive an escalating dose of Siponimod up to 1 mg/day (N=70) or placebo (N=35) for 12 months (Table 2). We conducted a power analysis for sample size determination using the reported data from brain volume changes in SPMS subjects treated for at least 12 months with Siponimod or placebo²⁵. We wished to fit a repeated measures ANOVA model with two treatment levels in drug vs. placebo, and 4-time measures to receiving the drug (i.e. vMRI at baseline, 6, 12, and 18 months). We defined $Y_{ij} = \mu + \alpha_i + \tau_j + (\alpha\tau)_{ij} + \varepsilon_{ijk}$, where Y_{ijk} denotes the measure on brain atrophy, α_i denotes the treatment effect $i = 1, 2$; τ_j denotes the time effect at time $j=1, 2, 3, 4$; $k = 1, n$; $(\alpha\tau)_{ij}$ is the interaction between time and treatment; and ε_{ijk} is the error term²¹. We study the effect of the drug on brain atrophy. The between-subject factor in our model is treatment, with two levels (study drug and placebo), and we allocate each treatment in the ratio 2:1. The within-subject factor is time, with four levels (0, 6, 12, and 18 months). The number of patients needed is determined to achieve a power of 0.90 at significance level $\alpha = 0.05$ for the test of the interaction between time and treatment, where the contrast over time contains all pairwise comparisons. We also intend to generate a plot of power versus sample size that covers the power range of 0.05 to 0.90.

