Summary statistics for actual values and for changes from baseline will be tabulated for laboratory results by scheduled visit. Subjects with clinical laboratory values outside of the normal reference range at any post-baseline assessment will be summarized. Shifts from baseline laboratory values (to worst severity per subject) will be tabulated.

- Electrocardiogram Results

The EKG parameters (heart rate, PR interval, QRS interval, QT interval, and QTc interval) at each time recorded (scheduled for screening and study end) as well as the change from screening will be summarized with descriptive statistics.

The overall EKG assessment will be reported as “Normal” or “Abnormal” with respect to relevant abnormalities by the investigator. A shift table comparing the EKG assessment over the treatment period (every abnormal) to screening will be presented.

- Vital Signs

The observed data at baseline and change from baseline for each measurement day will be summarized with descriptive statistics.

BASELINE DESCRIPTIVE STATISTICS

The distributions of patients completing each study visit and the reason for early terminations will be tabulated for each treatment group. The duration of double-blind treatment within each treatment group and compliance rates will be summarized by descriptive statistics (mean, standard error, standard deviation, median, minimum, maximum, and sample size) for days of treatment, for total days of exposure, and by the distributions of patients exposed to various durations of treatment categories. Demographic and baseline characteristics will be summarized by descriptive statistics for all patients in each treatment group.

PLANNED INTERIM ANALYSES

Formal interim analyses are not planned. Data will be reviewed by the DSMB for their assessment of safety and risk/benefit considerations.

SUB-GROUP ANALYSES

No sub-group analyses are planned.

TABULATION OF INDIVIDUAL PARTICIPANT DATA

Participant data will be listed by measure and time point.

EXPLORATORY ANALYSES

Statistical analysis of the exploratory CSF, blood, and saliva biomarkers will be carried out by our biostatistician. Comparisons will assess the change from baseline for the following markers assessed at the frequency indicated in the schedule of visits Table 1):

- Alzheimer's Disease Cooperative Study- Activities of Daily Living (ADCS-ADL)
- blood inflammatory markers (e.g., TNF- α , IL-1 β , IL-6)
- CSF and plasma C-reactive protein
- CSF and plasma TNF- α

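### Current and past anti-amyloid antibody users are enrolled alongside untreated patients, but antibody status enters neither the randomisation nor the models written in the protocol

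*Protocol*

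**What the plan says.** Inclusion criterion 16 (Protocol, Section 1, Synopsis) reads in part "ex. lecanemab, donanemab) for > 6 months or have discontinued monoclonal antibody medication"; past users must have been off the drug for more than six months. No cap is set on either group.

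On allocation, Section 5 states "No patient stratification and no interim analysis are planned" and gives the arm sizes: "35 will be randomly assigned to the placebo group, and 70 will be randomly assigned to the drug arm".

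On analysis, the repeated-measures model under Sample Size Determination (Section 12) has treatment, time and their interaction: "The between-subject factor in our model is treatment, with two levels (study drug and placebo". The blood-marker model under General Approach has treatment and a random subject effect. The endpoint paragraphs compare change from baseline and name no covariate. Concomitant medications are tabulated by group, and "No sub-group analyses are planned".

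On what the antibodies do, Section 6 says: "Recently the mABs, aducanumab and lecanemab, were approved on the biomarker endpoints of removing amyloid". The Synopsis and Section 4 list amyloid beta in CSF and saliva as exploratory readouts. The Synopsis presents the saliva measures as possible surrogate markers of efficacy, and Section 10 explores CSF, blood and saliva markers as proxies for efficacy.

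On stability of background treatment, Section 8 gives a specific rule for two drug classes: "The patient can be on stable doses of a cholinesterase inhibitor and/or memantine if it is stable for at least 90 days". It gives none for antibodies.

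**The concern.** The six-month limits in criterion 16 show that the protocol regards the timing of antibody treatment as relevant at entry. Nothing is then carried into allocation or into the written models. With 35 placebo patients, the share of antibody users can differ between arms by chance. For an amyloid marker, such a difference pushes in the same place that siponimod is being tested, so an observed arm difference would be harder to attribute. Leaving out a factor that explains between-patient variation also costs some precision. Stratification cannot be supplied later: once patients are allocated, an analysis plan can adjust but cannot restore balance.

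**Working it through.** **Arm sizes.** Section 12 needs 90–94 evaluable patients and allows about 10% attrition: 94 / (1 − 0.10) = 104.4, rounded up to 105. At 2:1 this gives 70 and 35, as stated.

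**Chance imbalance.** The documents give no figure for how many patients will use antibodies, so p = 10%, 20% and 40% is assumed. The standard error of the between-arm difference in use is SE = √[p(1 − p)(1/70 + 1/35)]. The last two columns are exact probabilities for the difference of two independent binomials.

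| Assumed use | SE (points) | 1.96 × SE | Gap ≥ 10 points | Gap ≥ 20 points |
|---|---|---|---|---|
| 10% | 6.2 | about 12 | 13% | 0.2% |
| 20% | 8.3 | about 16 | 26% | 2.0% |
| 40% | 10.1 | about 20 | 36% | 5.7% |

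CSF and saliva collection is optional, so those subsets are smaller. With an illustrative 20 versus 10 patients at 20% use, SE = √[0.16 × (1/20 + 1/10)] = 15.5 points.

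**Shift in the atrophy contrast.** Assume that antibody use changes annual atrophy by 20–40% of the placebo rate, in either direction; this is not in the documents. The shift is the gap times the effect.

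- 16-point gap (edge of the 95% range at 20% use): 0.16 × 0.20 = 3.2% to 0.16 × 0.40 = 6.4% of the placebo rate.
- One-SE gap: 0.083 × 0.20 = 1.7% to 0.083 × 0.40 = 3.3%.

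Section 12 conjectures a 20–30% effect. The 16-point gap is therefore worth between 3.2/30, about one tenth, and 6.4/20, about one third, of that effect.

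**The same on a standardised scale.** In a simple two-group comparison with 94 patients at 2:1, 90% power at two-sided 5% requires (1.960 + 1.282) × √(1/31.3 + 1/62.7) = 0.709 SD. Assume an antibody effect of 0.2–0.5 SD.

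- A 20-point gap shifts the contrast by 0.04–0.10 SD, which is 6–14% of 0.709.
- Given a 20-point gap, the unadjusted test with 31 versus 63 patients has a conditional type I error of about 5.9% (effect 0.3 SD) to 7.4% (0.5 SD).
- Omitting the factor inflates the variance by 1 + p(1 − p)d². For p = 20–50% and d = 0.3–0.5, power falls from 90% to about 88–90%.

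**The case against.** The strongest reply is that little of this touches what the trial is mainly for. The primary endpoint is safety. The only readout on which the protocol itself supports an antibody effect is amyloid, which is exploratory, with optional CSF and saliva sampling. Blood amyloid appears only in the Synopsis; Sections 4, 10 and 12 list inflammatory markers for blood. Any prognostic factor can be unbalanced with 35 patients, and tabulating concomitant medications would reveal an imbalance in current use. All of this stands and limits the weight of the point.

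Four stronger readings are tempting, and the documents do not support them.

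- **Antibodies act on the MRI endpoint.** No section says that they change hippocampal, cortical or whole-brain volume. Section 2.1 calls earlier attempts to lower neuroinflammation, among which it counts aducanumab and lecanemab, inconclusive on disease trajectory and cognitive decline. Section 8 says "Temporary discontinuation of treatment with study drug due to ARIA-E should not be considered as non-compliance", but this concerns interruption of study drug; neither it nor Section 10 ties these imaging findings to antibody use or to brain volume.
- **Antibodies may be started or stopped freely during the study.** Criterion 16 is itself an entry stability rule. Section 8 refers to stable standard-of-care treatment, asks patients to consult before any new medication or dose change, and refers drugs that may affect cognition to the medical monitor. What is absent is a rule specific to antibodies.
- **No adjustment will be made.** The vMRI model stands under sample size, and an analysis plan that is not shown may add covariates. The refusal of subgroup analyses does not exclude them. The firm point is the refusal to stratify, together with written models that lack the term.
- **The test is invalid.** Randomisation keeps the unconditional type I error at its nominal level.

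**Conclusion.** The point holds as a worthwhile improvement, not as a flaw that undermines the trial. The protocol knowingly mixes current, past and never users of drugs that it says remove amyloid, measures amyloid beta as a possible proxy for efficacy, and expressly declines to balance the arms on that factor. A gap of 10 points or more would arise in about 13–36% of randomisations at 10–40% use. The consequence is conditional bias and a small loss of precision: about 3–6% of the placebo atrophy rate for a 16-point gap, and at most about two points of power. These sizes rest on assumed prevalence and assumed antibody effects. The effect on amyloid markers cannot be sized from the documents, but imbalance there can be larger because the optional subsets are smaller.

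**What to change.** 1. In Section 5, replace the statement that there is no stratification with 2:1 permuted-block randomisation stratified by current anti-amyloid antibody use at Baseline (yes/no). If enrolment has started, leave the allocation as it is and adjust only.
2. In Section 12, prespecify antibody status (current, past, never) as a covariate in the vMRI, ADCOMS and amyloid-marker comparisons. The covariate is useful even with stratification, because the efficacy set is limited to patients who reach Visit 12 and the biofluid subsets are optional, so balance at randomisation need not carry over.
3. Take the status from the eligibility check and medical history. The concomitant-medication form covers drugs taken during the study, so it would not by itself identify past users.
4. Record the dates of any antibody start, stop or restart on study, and report a sensitivity analysis that uses only data before such a change.

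Cost: the biostatistician re-issues one randomisation list at a single site, with some incomplete blocks and one or two degrees of freedom in the models. Eligibility and treatment are unchanged.

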1.1 STUDY PROCEDURES

Visit 1, Day -56 to 0 Screening Visit (Up to 8 weeks)

During the screening visit, the subject (or their legally authorized representative as appropriate) and study partner / informant (if not the same as their LAR) will sign the informed consent document prior to undergoing any study procedures.

The following tests and evaluations are used to determine subject eligibility:

- Informed consent
- Inclusion and exclusion criteria
- *CYP2C9* genotyping (buccal swab)
- Medical History & Verify Diagnosis
- Concomitant medication reconciliation
- Serum pregnancy test if applicable
- Neurological and physical examination
- Vital signs, height and weight
- Labs (CBC, CMP, Hep B, Hep C, HIV, TSH)
- Coagulation panel (PT, PTT, INR) (optional, only for patients who opt into LP/CSF substudy)
- Cognitive assessments (MMSE, Hachinski, GDS)
- Columbia Suicide Severity Rating Scale (C-SSRS)
- MRI (MRI or CT within the past 12 months of Screening Visit Day 1)
- EKG (electrocardiogram)

Patients who do not meet the eligibility criteria will not be randomized and will be considered screen failures. Screen failures may be re-screened once per PI discretion for eligibility..

If no MRI or CT scan has been completed within the past 12 months: Participants who consent will be scheduled for volumetric MRI (vMRI) to be completed prior to the Baseline Visit.

In addition, participants will be asked to complete an ophthalmic evaluation to obtain a baseline evaluation prior to the start of treatment.

Optional Lumbar Punctures for CSF Sub-Study

For lumbar punctures, the principal investigator (or sub-investigator) will perform the procedure. A separate section will be added to the consent form, which the subject (or their legally authorized representative) will sign to authorize the lumbar puncture and collection of cerebrospinal fluid (CSF). To ensure subject safety, PT, INR, and PTT levels will be checked at baseline prior to any lumbar puncture procedure and subsequently prior to each follow-up visit where a lumbar puncture is being performed.

A follow-up telephone check will be conducted the day after each lumbar puncture within 24-48 hours. If there is persistent spinal headache, a blood patch may be administered at the discretion of the investigator.

Optional Saliva Sub-Study

Participants will have the option to provide a saliva sample via passive drooling at Baseline, Week 24, Week 52, Week 56 and Week 78. We will measure A β 40 and A β 42 in all saliva samples, as done previously³⁷.

Visit 2 at Day 1 of dosing, Baseline Visit, 0.25mg/day

Upon confirmation that all eligibility criteria have been met, baseline evaluations will be performed with subjects. These evaluations will include an assessment of concomitant therapy/medications, measurement of vital signs and body weight, collection of blood samples, vMRI (if not performed at screening) and cognitive assessments.

The following procedures and tests will be performed at baseline:

